	
Alpha-Stim AID Cranial Electrotherapy Stimulations (CES) for participants with a primary working diagnosis of generalised anxiety disorder (GAD), in terms of health and social care service cost, and patient cost, from baseline to week 24, following previous treatment with low intensity psychological therapy intervention.
	
See Appendix B
 
The CSRI, adapted for use for anxiety disorders in primary care and community settings, is a measure of the full health and social care cost and patient cost of treatment.
 
The endpoint will be the cost impact from baseline to week 24.
 
EQ-5D-5L
 
See Appendix C
 
The EQ-5D-5L is a participant-reported measure of health utility and quality of life used by NICE to generate QALYs for cost effectiveness assessments. The EQ-5D-5L uses 6 items.
 
The endpoint will be the change in EQ-5D-5L for participants from baseline to week 24.
 
Work and Social Adjustment Scale (WASA)
 
See Appendix D
 
The WASA scale is a participant-reported measure of work and social function. The WASA scale uses 5 items.
 
The endpoint will be the change in WASA scale score for participants from baseline to week 24.

Tertiary
	
The tertiary objective of this study is to evaluate the clinical effectiveness of treatment with Alpha-Stim AID Cranial Electrotherapy Stimulations (CES) for depression and insomnia in participants with a
	
PHQ-9
 
See Appendix E
 
The PHQ-9 is a participant-reported measure of depressive symptomatology.

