Alpha-Stim AID is a CE marked medical device which has been registered as an approved product since 11 May 1998. Alpha-Stim AID is marketed for the alleviation of psychological conditions including anxiety, insomnia and depression, through using cranial electrotherapy stimulations (CES) which are tiny electric currents applied through ear clips. The treatment provided by the device is non-invasive, non-pharmacological, and can be used as adjunctive treatment to step one, two and three treatment intervention. Pregnancy, implantation with a pace maker and implantation with an implantable cardioverter device (ICD) are contraindications.

Alpha-Stim AID CES could therefore compliment psychological treatment in the IAPT care pathway, through acting as an effective maintenance treatment, and to act as adjunctive treatment to improve the clinical effectiveness of step three high intensity psychological therapy intervention. Improved effectiveness could reduce the requirement for additional psychological and pharmacological treatment, thus reducing cost within the health and social care system (primarily within the IAPT services but also within primary care), thus enabling the IAPT service to maintain capacity to deliver high intensity psychological therapy intervention.

This study will recruit 120 participants from Leicestershire and Rutland IAPT service (under the organisation of Nottinghamshire Healthcare NHS Foundation Trust). These participants will have a primary working diagnosis of moderate-to-severe GAD, and will have received step two low intensity psychological therapy intervention within an IAPT service but received no improvement (continued to be classified as moderate-to-severe GAD) from these interventions.

So as to place the study in the context of a systematic review of relevant studies, the following information provides background to the clinical effectiveness of CES treatment generally, and then specifically for anxiety, depression and insomnia.

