#### 3.4 Primary outcome measures

The primary objective will be measured using GAD-7 scores, which is a participant-reported screening tool and severity measure for generalised anxiety disorder (GAD).

- The outcome measure for **reliable improvement of GAD** is defined as participants who reach a score reduction of 5 or more from baseline to week 24. Such a reduction amounts to a clinically important change. Some reliable improvement is defined as participants who reach a score reduction of 1 – 4 from baseline to week 24. No reliable improvement is defined as participants who reach no score reduction from baseline to week 24.
- The outcome measure for **clinically significant improvement of GAD** is defined as participants with a score of 10 or more at baseline, who reach 9 or fewer by week 24.
- The outcome measure for **recovery of GAD** is defined as participants with a score of 10 or more at baseline, who reach 7 or fewer by week 24.

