#### 3.5 Secondary outcome measures

The secondary objective will be measured using the Client Service Receipt Inventory (CSRI), adapted for use for anxiety disorders in primary care and community settings, which is a measure of the full health and social care cost and patient cost of treatment. Additionally, the objective will be measured using the EQ-5D-5L, which is a participant-reported measure of health utility and quality of life used by NICE to generate QALYs for cost effectiveness assessments, and uses 6 items. Finally, the objective will be measured using the Work and Social Adjustment Scale (WASA) which is a participant-reported measure of work and social function, and uses 8 items.

- The outcome measure for **CSRQ** is the change in cost impact for previous 12 weeks from baseline to week 24.
- The outcome measure for **EQ-5D-5L** is the change for participants from baseline to week 24.
- The outcome measure for **WASA** is the change for participants from baseline to week 24.

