## **11 STATISTICS AND DATA ANALYSIS**

### **11.1 Sample size calculation**

If Alpha-Stim AID CES has a comparable effect to IAPT high intensity psychological therapy interventions in patients with a primary working diagnosis of GAD, it will achieve an effect size of 1.04 (95% CI 0.88 to 1.23) in an intention to treat sample of 4,183 participants with pre-treatment GAD-7 score of 14.06 (s.d. 5.11) and post treatment GAD-7 score of 8.10 (s.d. 6.37) (Richards and Borglin, 2011). Reliable improvement was obtained after IAPT treatment for generalised anxiety disorder in 54.7%, reliable improvement plus clinically significant change in 40.1% and recovery in 46.0%.

However, to make a meaningful economic impact on NHS care, then Alpha-Stim AID CES does not need to be as effective as IAPT high intensity psychological therapy interventions. In a previous randomised controlled trial (Barclay and Barclay 2014), Alpha Stim CES reduced the mean Hamilton Anxiety score from 29.5 to 13.4 while sham Alpha Stim CES reduced it from 27.6 to 20.0 over 5 weeks  $p=0.001$ ,  $d=0.94$ , with 83% patients showing a drop of 50% in HAM-A score.

A meta-analysis of 14 Alpha Stim CES randomised controlled trials estimates an average effect size of 0.60. On this basis reliable improvement may be seen in 33%, reliable improvement plus clinically significant change in 24% and recovery in 28% cases.

The cost of IAPT high intensity psychological therapy intervention is estimated to be £2,895.00 per participant and £2,914.00 if stepped care was involved (Radhakrishnan et al, 2013). On a cost offset basis if Alpha-Stim AID CES cost £465.00, then reliable improvement plus clinically significant change (which would not necessitate high intensity treatment) in only 20% would be clinically and cost effective.

Taking all data into account, 60 patients would be required to complete Alpha Stim AID CES treatment and all assessments. However, to allow for drop-out from assessments, drop-out from Alpha-Stim AID CES, and choice in relation to IAPT high intensity psychological therapy intervention ,120 patients will be recruited.

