### **11.3 Statistical analysis plan**

Mean and standard deviation scores will be reported for each visit time-point. The statistician who will deliver the analysis is:

[name]., PStat  
Professor – Psychometrics & Statistics  
Accredited Professional Statistician - American Statistical Association  
Director – Initiative for Interdisciplinary Research Design & Analysis (IIRDA)  
Texas State University  
[name]  
Email: [[contact]](mailto:[contact])

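### Section 11.3 plans only a mean and SD per visit, which gives neither the precision of the week 24 change endpoints nor the primary responder proportions, and can mix change with who is observed if loss is related to scores

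*Combined protocol and SAP*

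**What the plan says.** Apart from naming the statistician, section 11.3 consists of one sentence: "Mean and standard deviation scores will be reported for each visit time-point".

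The endpoints are defined elsewhere, and none of them is a visit mean:
- **EQ-5D-5L and WASA.** In section 3.5 the outcome for each "is the change for participants from baseline to week 24". The Study Summary agrees: "The endpoint will be the change in EQ-5D-5L for participants from baseline to week 24" and "The endpoint will be the change in WASA scale score for participants from baseline to week 24".
- **GAD-7 (primary).** Section 3.4 counts, for reliable improvement, "participants who reach a score reduction of 5 or more from baseline to week 24". Clinically significant improvement and recovery are threshold crossings in people scoring 10 or more at baseline.
- **PHQ-9 and Athens.** Section 3.6 defines them by each participant's own reduction or threshold crossing.

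On numbers, section 11.1 states that "60 patients would be required to complete Alpha Stim AID CES treatment and all assessments" and that 120 are recruited to "allow for drop-out from assessments, drop-out from Alpha-Stim AID CES, and choice in relation to IAPT high intensity psychological therapy intervention". Sections 7.7 and 7.8 ask for best efforts to re-establish contact and keep data collected before withdrawal. No section gives an analysis of change, a confidence interval, an analysis set, a responder denominator for the analysis, or a method for missing visits.

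**The concern.** The plan's only analysis does not produce the plan's endpoints. Three things are at stake.

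1. The change in EQ-5D-5L and WASA would be reported without a valid measure of precision. Its standard error depends on the within-person correlation, which visit SDs do not contain.
2. If the baseline mean covers everyone enrolled and the week 24 mean covers only those still answering, their difference can combine real change with a change in who is observed. The study has one arm, so no control group can offset this.
3. The primary GAD-7 outcome is a set of proportions. These cannot be recovered from means and SDs, however complete the follow-up.

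Section 10.3 says the final report is mainly meant as evidence for NICE and NHS England, so an estimate of change with its uncertainty is what readers will look for.

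**Working it through.** **Inputs**
- Recruited 120, required completers 60 (section 11.1).
- GAD-7 SDs of 5.11 before and 6.37 after treatment, from the cohort cited in section 11.1. They are used here only as an illustration.
- Anticipated reliable improvement in 40 of 120, or 33% (section 11.1).
- Assumptions, because the documents give no figure: the within-person correlation, the retention, and the baseline gap between those who stay and those who leave.

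**The plan's own figures.** 60 / (1 − 0.50) = 120, so the recruitment target implies an allowance of 50% for not completing treatment and all assessments. The rate is implied, not stated. The anticipated reliable improvement reproduces as 54.7% × 0.60 = 32.8%, and 33% of 120 = 39.6, i.e. 40.

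**Precision of change**

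SD of change = √(5.11² + 6.37² − 2 × r × 5.11 × 6.37); 95% half-width = 1.96 × SD / √n.

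| r (assumed) | SD of change | Half-width, n = 120 | Half-width, n = 60 |
|---|---|---|---|
| 0 | 8.17 | 1.46 | 2.07 |
| 0.3 | 6.87 | 1.23 | 1.74 |
| 0.5 | 5.84 | 1.05 | 1.48 |
| 0.7 | 4.60 | 0.82 | 1.16 |

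Every row has the same two visit SDs. Reporting only those SDs leaves the reader unable to choose among the rows, even with all 120 followed.

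**Composition shift**

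For means over available participants, this identity is exact:

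(week 24 mean of those observed) − (baseline mean of all) = (mean paired change of those observed) + (share lost) × (baseline mean of stayers − baseline mean of leavers).

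Suppose leavers start 2 GAD-7 points worse (assumed), and no one who stays changes:
- 90% retention: 0.10 × (−2) = −0.2
- 75% retention: 0.25 × (−2) = −0.5
- 50% retention: 0.50 × (−2) = −1.0

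If leavers start 2 points better, the signs reverse. If the baseline gap is zero, or nobody is lost, the shift is zero. For scale, the reliable-improvement threshold in section 3.4 is 5 points.

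**Is paired change among those observed enough?** It removes the composition term but not selection. A simulation used no mean change, SD 5.11 at both visits, 50% retention and correlation 0.3 to 0.7 (all assumed):

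| Loss depends on | Difference in visit means | Paired change in completers |
|---|---|---|
| Nothing | about 0 | about 0 |
| Baseline score | −0.35 to −1.47 | +0.37 to +1.47 |
| Week 24 score | −1.2 to −2.1 | −0.37 to −1.47 |

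So an analysis that uses all enrolled participants is preferable to one of completers only.

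**Responder proportions.** Two samples can share a mean and SD at each visit and yet differ in the share who fall by 5 or more, so section 3.4 needs its own analysis. The denominator matters too. At the 50% ceiling, with 33% of 60 observed participants responding (19.8), the proportion among all 120 could lie between 19.8/120 = 16.5% and (19.8 + 60)/120 = 66.5%.

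**The case against.** A reader might draw four stronger conclusions, and the documents do not support them.

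- **That half the sample will be missing at week 24.** The allowance in section 11.1 pools three reasons without splitting them, and stopping the device or choosing about therapy need not lose a questionnaire. Sections 7.5 and 7.6 schedule all five scores at weeks 8, 12 and 24 whether or not the device is continued, and section 7.7 asks for full data collection. Fifty per cent is an upper bound, and actual loss may be much smaller.
- **That visit means cannot estimate change.** With complete data their difference equals the mean within-participant change exactly. With loss unrelated to scores it is unbiased. Bias needs score-related loss, and it can go either way.
- **That the plan has chosen available-case means.** Section 11.3 names no analysis set. Available cases is the natural reading, but it is an inference.
- **That the fall in means is the trial's main evidence.** The primary outcome is responder status, and section 11.1 anticipates counts out of 120.

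Other objections also have force. The 2-point gap is assumed and carries different weight on GAD-7 (0 to 21) and WASA (0 to 40). For EQ-5D-5L the documents give no SD, so no figure is offered. The SD of 5.11 comes from a cited cohort, while enrolment requires a baseline GAD-7 of 10 or more, so the baseline spread here is probably narrower: an even spread over 10 to 21 has an SD of about 3.45. For this reason the shift above is given in points, and the precision and simulation figures are illustrations. Finally, an unstructured covariance over six visits has 6 × 7 / 2 = 21 parameters, and a simpler model could be defended.

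None of this supplies the missing analysis of change, its precision, or the responder proportions.

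**Conclusion.** The point holds in a conditional form. Two parts do not depend on drop-out: visit SDs cannot give the standard error of the EQ-5D-5L and WASA change, and visit means cannot give the primary GAD-7 proportions. On the illustrative SDs, the unknown correlation alone moves the half-width from 1.46 to 0.82 GAD-7 points with 120 followed.

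The third part rests on two assumptions: that means are taken over available participants, and that loss is related to scores. Under them, a 2-point baseline gap shifts the apparent change by 0.2 to 1.0 GAD-7 points between 90% and 50% retention, in either direction, with the largest value at a ceiling that the study may not approach. Without score-related loss there is no bias. The plan should be changed, but the documents do not show that its visit means will mislead.

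**What to change.** In section 11.3:

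1. For each continuous score (EQ-5D-5L, WASA, GAD-7, PHQ-9, Athens), report the within-participant change from baseline to each visit with a 95% CI. Take it from a repeated-measures mixed model on all enrolled participants and all six visits, with visit as a factor and an unstructured covariance. Name in advance a simpler structure to use if the model does not converge.
2. Keep the visit means and SDs, and print beside each one the n and the baseline mean of the participants who contribute to it. A composition shift is then visible.
3. Report the GAD-7, PHQ-9 and Athens responder proportions with 95% CIs. For GAD-7 reliable improvement the denominator is all enrolled (120, as in the counts anticipated in section 11.1). For threshold outcomes it is those meeting the baseline cut-off. State the denominator for PHQ-9 and Athens reliable improvement as well, since those definitions have no cut-off. Count a missing week 24 score as non-response, and add an observed-case sensitivity analysis.

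The cost is SAP wording and a little more analysis; section 7.6 already schedules all five scores at all six visits. The model assumes that data are missing at random. This is weaker than what raw visit means need, but it still fails if loss depends on unobserved week 24 scores. Counting missing as non-response lowers the proportions when loss is substantial, which is why the observed-case analysis should stand beside it.

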## **12 DATA HANDLING**

### **12.1 Data collection tools and source document identification**

The data collection tools are:

- GAD-7
- EQ-5D-5L
- CSRI
- WASA
- PHQ-9
- Athens Insomnia Scale
- Anxiety log

The research nurse will administer these and record the data as follows:

- Enter the data directly into the electronic patient record (PCMIS) – GAD-7, WASA and PHQ-9 are currently established within PCMIS. In this scenario, PCMIS record acts as the source document. A copy of the anonymised PCMIS data will then be emailed to the sponsor.

**OR**

- Enter the data into a CRF – EQ-5D-5L, CSRI, and Athens are not currently established within PCMIS. In this scenario, the CRF acts as the source document. The source document will be scanned into PCMIS, and a copy will then be emailed to the sponsor. It is anticipated that the CRF will act as source documentation for all assessments, regardless of establishment within PCMIS.

**OR**

- Participant will enter data into the anxiety log, and send this to the research nurse at week 6 or week 12. The anxiety log will act as the source document, and will be scanned into PCMIS, and a copy will then be emailed to the sponsor.

### **12.2 Data handling and record keeping**

Participant in the study will be confidential. Only IAPT staff who are part of the patient's routine care team will have access to personal information prior to the patient indicating interest in the study and arranging a baseline visit with the research nurse.

When consent is received, participants will ask to agree for IAPT staff, host institution, authorised representatives of the Sponsor and regulatory authorities to have access to participant's medical records for the purpose of monitoring and audit.

Source data will be retained at site, and copies will be sent in hard copy via email to the Sponsor, whereby data will be inserted into the study database. Study database will be maintained by the Sponsor, and will be stored anonymously at all times. It will not be possible to identify participants from the information stored, and no identifiable information will be used in any publications. Data will be emailed within 3 working days of the participant visit.

### **12.3 Archiving**

The TMF will be retained by the sponsor legal representative, and the ISF will be retained by the host site. Both the TMF and ISF must be archived for a minimum of five years post study end date. Sponsor legal representative will notify the host site when essential documents may be destroyed.

## **13 AUDIT**

Data will be monitored for quality by the sponsor, sponsor legal representative or delegated representative throughout the study to ensure consistent data collection.

## **14 ETHICAL AND REGULATORY CONSIDERATIONS**

### **14.1 Approvals**

Prior to enrolling participants, the study will be submitted to the HRA for REC and legislation compliance reviews. The study will not enrol participants until receipt of REC favourable opinion, HRA Approval, and local confirmation of capacity and capability from Nottinghamshire Healthcare NHS Foundation Trust. Competent Authority approval is not required.

The study will comply with all approval requirements, including the requirement for registration to a publically accessible database. The study will be registered to clinicaltrials.gov within 6 weeks of recruitment of the first participant.

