## **7.5 Study assessments**

At baseline, participants will agree with the research nurse a convenient time and date for the visits undertaken via telephone. Visits should be undertaken within 5 calendar days of the exact date.

Additional visits are undertaken at 4 weeks post baseline, 6 weeks post baseline, 8 weeks post baseline, 12 weeks post baseline and 24 weeks post baseline.

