### **Visit 2: Week 4 (plus or minus 5 calendar days)**

The research nurse will telephone call the participant and undertake the following assessments:

- GAD-7
- EQ-5D-5L
- WASA
- PHQ-9
- Athens Insomnia Scale
- Check treatment compliance and anxiety log completion
- Check adverse events

The research nurse will administer these and record the data either directly into the electronic patient record (PCMIS) if available (and therefore the PCMIS record will act as source data), or into a Case Report Form (CRF) if not available (and therefore the CRF will act as source data) and then transpose the data into PCMIS or scan the CRF into the electronic file.

It is anticipated that these assessments will take approximately 30 minutes in total.

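### Section 14.1 lets public registration follow the first recruit by up to six weeks, so no public record of the outcomes need exist before the sponsor sees early on-treatment scores

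*Combined protocol and SAP*

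**What the plan says.** Section 14.1 sets the gate for enrolment: "The study will not enrol participants until receipt of REC favourable opinion, HRA Approval, and local confirmation of capacity and capability". Public registration is not part of that gate. It is promised separately: "The study will be registered to clinicaltrials.gov within 6 weeks of recruitment of the first participant".

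Section 12.2 governs when and where data arrive: "Data will be emailed within 3 working days of the participant visit", and "Study database will be maintained by the Sponsor, and will be stored anonymously at all times". Section 7.5 places the first follow-up contacts: "Additional visits are undertaken at 4 weeks post baseline, 6 weeks post baseline", with later ones at weeks 8, 12 and 24, and "Visits should be undertaken within 5 calendar days of the exact date". The week-4 call collects GAD-7, EQ-5D-5L, WASA, PHQ-9 and Athens scores.

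Section 3.4 defines the primary outcome as three GAD-7 criteria from baseline to week 24 (reliable improvement, clinically significant improvement, recovery), each with a numeric cut-off and none placed first. The analysis described in section 11.3 is one sentence: "Mean and standard deviation scores will be reported for each visit time-point".

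**The concern.** Prospective registration gives readers outside the study a dated public statement of what would be reported, made before anyone had seen a result. The rule in 14.1 does not secure that. Every participant receives the device, and section 4 describes neither a control arm nor blinding, so each follow-up GAD-7 score shows change on treatment directly. The coded IDs in 14.6 hide who the participant is, not how the score moved.

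There is also room for choice in what to emphasise. Three GAD-7 criteria share primary status, GAD-7 is taken at six visits, and section 11.3 names no headline visit or measure and does not mention responder proportions. Participants may start high intensity therapy after the minimum 6 to 8 week wait (section 7), so results at weeks 6, 12 and 24 do not carry the same meaning.

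The evidence is intended for NICE and NHS England (sections 2 and 10.3). The sponsor supplies the device (8.3). Its legal representative sells the device, funds the study and writes the manuscript (8.2 and Role Delegation). A public record that predates all scores would be a simple safeguard in that setting.

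**Working it through.** The plan gives no figure of its own to reproduce. The check is calendar arithmetic.

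**Inputs**
- Registration limit: 6 weeks = day 42 after the first recruit (14.1).
- Week-4, week-6 and week-24 visits: days 28, 42 and 168, each ±5 days (7.5).
- Transfer: 3 working days, which is 3 to 5 calendar days, or 0 if sent the same day (12.2).
- Sample and window: 120 participants (11.1), 01 September 2016 to 01 March 2017 = 181 days (7.9).
- Assumption: uniform accrual with the first recruit at day 0. The plan gives no accrual curve.

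**When the first participant's scores reach the sponsor**

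Day held = visit day ± window + transfer.

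| Score | Earliest | Latest | Held by day 42? |
|---|---|---|---|
| Week 4 | 28 − 5 + 0 = 23 | 28 + 5 + 5 = 38 | Always |
| Week 6 | 42 − 5 + 0 = 37 | 42 + 5 + 5 = 52 | Sometimes |
| Week 24 | 168 − 5 + 0 = 163 | 168 + 5 + 5 = 178 | Never |

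These dates do not depend on the accrual rate.

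**How many participants**

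Rate = 120 / 181 = 0.663 per day, or 4.64 per week.

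- Enrolled by day 42: 0.663 × 42 = 27.8, about 28 (28 / 120 = 23%).
- Scores held = 0.663 × (42 − day held), plus 1 if the day-0 recruit is counted separately.
- Baseline scores, transfer 0 to 5 days: 0.663 × 42 = 27.8 down to 0.663 × 37 = 24.5, or 28.8 down to 25.5 with the first recruit added. That is about 25 to 29.
- Week-4 scores, visits on time, transfer 3 days (held day 31): 0.663 × 11 = 7.3, or 8.3 with the first recruit.
- Week-4 scores, visits on time, transfer 5 days (held day 33): 0.663 × 9 = 6.0, or 7.0. With the line above, this gives about 6 to 8.
- Week-4 scores at the extremes, first recruit counted: 0.663 × 19 + 1 = 13.6 (held day 23) and 0.663 × 4 + 1 = 3.7 (held day 38), so roughly 4 to 14.
- Week-6 scores, at most: 0.663 × 5 + 1 = 4.3, and none for on-time visits with 3 or more days' transfer.

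**Distance from the primary endpoint**

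163 − 42 = 121 days, about 17 weeks between the registration limit and the earliest possible week-24 score.

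**After the change**

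With registration before the first consent, the sponsor holds no participant scores when it registers.

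**The case against.** The best defence is that the outcomes are already fixed, in writing and outside the sponsor, before anyone is enrolled. Sections 3.4 and 3.6 give week-24 definitions with numeric cut-offs. The version control table dates version 2.0 to 28 July 2016, ahead of the planned opening on 01 September 2016. Enrolment waits for REC and HRA decisions, and section 14.9 requires amendments to be notified to both. This stands, and it limits the point to the public record. A reader might infer that the choice of week 24 is still open, but the protocol states it consistently in section 3.

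Three other strong readings are tempting:
- **The primary results could be seen before registration.** They could not: no week-24 score can exist until about day 163.
- **Registration was in fact late.** The wording sets an outer limit and allows earlier registration. The documents do not show when it took place.
- **The loss could never be made good.** Releasing the dated protocol with its version history would let a reader compare reported outcomes with those set before enrolment. What cannot be recreated afterwards is a public entry that predates the data.

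It is also fair to say that the thin section 11.3 and the three co-equal criteria are analysis-plan problems, which earlier registration would record but not cure. They bear on this point only because they leave more for a public record to pin down. Finally, nothing else in the documents contradicts the six-week allowance. This is an improvement to the design, not a correction of an internal error.

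**Conclusion.** The point holds in a limited form. The rule in 14.1 permits registration after the sponsor has received on-treatment outcome scores. For the first participant this is so at every permitted visit and transfer time, provided the sponsor waits until near the limit. The exposure would then be baseline scores for most of about 28 participants and week-4 scores for about 6 to 8 (roughly 4 to 14), with perhaps a few week-6 scores and no week-24 scores.

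The counts rest on uniform accrual from day 0, and slower early recruitment would lower them. At half the rate, for example, 0.331 × 42 = 13.9 would be enrolled by day 42. The arrival of the first week-4 scores by about day 38 does not rest on that assumption.

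The documents give no ground for saying that outcomes were chosen after results were seen. What they show is that no public statement of the outcomes need exist before early scores are visible, in a study where such a statement would be useful and is already promised.

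**What to change.** Amend section 14.1 so that the study is registered on clinicaltrials.gov before the first participant is consented. The entry should state the primary outcome, the week-24 time point and the responder definitions from section 3.4. List registration with REC favourable opinion, HRA Approval and local confirmation as a condition for opening recruitment.

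If the three GAD-7 criteria remain co-equal, the entry should say so. Ranking them is a separate change to sections 3.4 and 11.3.

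The cost is only that of completing a promised registration a few weeks sooner. Sample size, visits, treatment and data flow are unaffected.
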